### **9.2.4. Adverse Event Reporting**

Adverse Events are unfavorable changes in health that occur in trial participants during the clinical trial or within a specified period following the trial.

For this clinical trial, adverse events include any adverse event that occurs as a result of the use or potential use of the study device. An investigator shall submit to the sponsor and to the reviewing Institutional Review Board (IRB) a report of any unanticipated adverse events, no later than 10 working days after the investigator first learns of the effect (21 CFR 812.150(a)(1)). A sponsor who conducts an evaluation of an unanticipated adverse device effect under 812.46(b) shall report the results of such evaluation to the Food and Drug Administration (FDA) and to all reviewing IRB's and participating investigators within 10 working days after the sponsor first receives notice of the effect. Thereafter the sponsor shall submit such additional reports concerning the effect as FDA requests (21 CFR 812.150(b)(1)).

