## 1.1. Synopsis

Title:	Traumatic Nightmares Treated by NightWare (To Arouse Not Awaken): A Randomized Controlled Trial
Study Description:	
This is a double-blinded, sham-controlled, randomized controlled trial to establish the safety and efficacy of the NightWare (NW) digital therapeutic system (NW System) which is to be used for the treatment of sleep disturbances related to nightmares associated with post-traumatic stress disorder (PTSD). This system consists of a Smartphone, a Smartwatch, and a proprietary application. This study will compare the Active System, which monitors sleep and provides tactile stimulation to terminate nightmares, to the Sham System that while it does monitor sleep, does NOT provide intervention but is otherwise identical. This study seeks to determine the safety and efficacy in treating PTSD-related sleep disturbance with the NW System as well as delineating the impact of improved sleep when using the Active System versus the Sham System.
 
The investigators hypothesize that the Active System will significantly improve sleep quality in subjects with PTSD-related sleep disorders who are suffering from nightmares and poor sleep quality, and that the magnitude of improvement will be greater than that observed in the subjects who receive a Sham System.

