### 4.1. Treatment Assignment

Any subject meeting all inclusion and no exclusion criteria is eligible for enrollment in the study. Subjects are considered enrolled in the study once the informed consent form (ICF) and Health Insurance Portability and Accountability Act (HIPAA) form have been executed.

All subjects will receive a NW System (research phone, research watch, and NW proprietary application-set to either an active mode or a sham mode). 240 subjects will be enrolled into the study. Subjects will be randomly assigned to receive either the Active System or Sham System. There will be 120 subjects in each arm. None of the subjects will be aware of whether they have received an Active System or a Sham System. For further details of treatment assignment procedures, go to the “Randomization” section of this protocol.

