### **9.2.3. Serious Adverse Event (SAE) Reporting**

A Serious Adverse Event (SAE) is an untoward occurrence in human research that results in death, a life-threatening experience, inpatient hospitalization, prolongation of hospitalization, persistent or significant disability or incapacity, congenital anomaly, or birth defect, or that requires medical, surgical, behavioral, social, or other intervention to prevent such an outcome (VHA Handbook 1058.01§4.r and 21 CFR 312.32(a)).

Only adverse events and deaths occurring at the site that are 1. serious **and** 2. unanticipated **and** 3. related or probably related to the research need to be reported to the IRB (VHA Handbook 1058.01 §6.a. & 6.b.)

If the event satisfies ALL three of these criteria the event must be reported to the IRB **within 5 business days** of learning of the event. The study sponsor will also be notified within the same time frame.

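### Section 9.2.4 ties this trial's adverse events to the device, and no adverse event schedule or by-arm table exists, so an all-cause Active versus Sham comparison to Day 30 is not assured

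*Protocol*

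**What the plan says.** The Synopsis describes a sham-controlled "randomized controlled trial to establish the safety and efficacy of the NightWare (NW) digital therapeutic system". On allocation, section 4.1 states "All subjects will receive a NW System" and "There will be 120 subjects in each arm".

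Section 9.2.4 contains two definitions in succession. The general one has no causal condition: "Adverse Events are unfavorable changes in health that occur in trial participants during the clinical trial or within a specified period following the trial". The trial-specific one reads: "adverse events include any adverse event that occurs as a result of the use or potential use of the study device".

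Section 9.2.3 defines seriousness by outcome, again without a causal condition: "A Serious Adverse Event (SAE) is an untoward occurrence in human research that results in death", followed by the other usual outcomes. Its reporting duty is narrower. Only events that are serious, unanticipated and at least probably related go to the IRB, with notice to the sponsor in the same time frame. Section 9.3 applies the same three criteria to deaths.

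The safety analyses in section 7.5, repeated in the SAP, are one-sample t-tests of ESS and C-SSRS change for the Active System. Neither document describes an adverse event table.

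**The concern.** A blinded sham arm means that nobody has to decide case by case whether the device caused an event. All events are counted in both arms and the difference answers the question. A definition that admits an event only when it is thought to result from the device puts the causality judgment ahead of recording. Section 6.4 keeps study staff blind to the device mode, so they would make that judgment without knowing whether the watch was delivering overnight stimulation.

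The events most easily lost are those that nobody connects with a watch worn at night, such as a fall, a daytime accident or a hospital admission. The filter may also work unequally, because a participant who notices vibration at night may be readier to link an event to the watch.

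The loss could not be made good later. Sham participants cross over to active treatment at Visit 2, so the randomised safety comparison exists only up to about Day 30.

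**Working it through.** The documents state no adverse event rate, margin or power, so there is no figure to reproduce and no arithmetic that would measure the point. The check is a comparison of passages.

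**1. Does the second sentence in 9.2.4 narrow the first?** A device-caused event is already an unfavourable change in health. Read as an addition, the trial-specific sentence adds nothing; it has a function only if it narrows. Section 9.2.1 has a parallel trial-specific sentence for unanticipated problems, and that one says expressly that its list is not exhaustive. Section 9.2.4 lacks that qualifier. Narrowing is thus the more natural reading, but it remains an inference. At the least, sites have two definitions that can lead to different records.

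**2. Does another passage restore all-cause capture?**

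| Place | What it provides | All-cause events by arm? |
|---|---|---|
| 1.3 Schedule of Activities | No adverse event row | No |
| 6.7 to 6.14 contacts | Named questionnaires and device-support calls; no adverse event question named | Not specified |
| 8.1 Withdrawal | Open adverse events are to be closed or marked chronic | Implies a record, does not define its content |
| 9.2.3 and 9.3 | Duty for serious, unanticipated and related events, and deaths meeting all three | No |
| 9.2.4 reporting duty | Unanticipated events only | No |
| 7.4 Interim Monitoring | Demographics and primary endpoint only | No |
| 7.5 and SAP | One-sample tests of ESS and C-SSRS | No |
| 7.6 and SAP | Between-group analyses of the surveys | Surveys only |

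**3. Which harms are covered anyway?** These measures are scheduled without restriction by arm:
- ESS and C-SSRS at Days 0, 30, 60 and 90.
- PHQ-9 at Days 0, 14, 30, 60 and 90.
- The daily questionnaire on Days 1 to 90, which asks about device disruption and nightmare-related awakenings.

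Sleepiness, suicidality, depressive symptoms and part of tolerability can therefore be compared between arms. Falls, accidents and all-cause hospitalisations have no instrument and no stated route into a by-arm count.

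**The case against.** The strongest reply is that the protocol does not say adverse events are limited to device-caused ones. The verb is an inclusive one and it follows an all-cause definition. The relatedness condition in 9.2.3 governs what must be reported, not what is recorded, and section 8.1 presupposes a site record of adverse events. The contents of the start-up and help-call questionnaires and of the REDCap forms are not in the documents, so an adverse event question may exist there. Section 7.6 and the SAP also plan between-group analyses of the surveys, and the Synopsis lists an Active versus Sham comparison of depression symptoms, so between-arm information on harms is not confined to the one-sample tests.

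Most of this stands, and it limits the claim. It shows that exclusion is not certain. It does not show that all-cause capture is specified anywhere, and it supplies no by-arm adverse event analysis.

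A reader might go further and infer that adverse events cannot be compared between arms at all, or that sham participants cannot have device-related events. The documents do not support either. Sham participants wear the same watch, and under section 2.3 it vibrates when they press START; only overnight stimulation is absent. Device-attributed events can therefore arise and be counted in both arms under the blind. What is at risk is the all-cause comparison.

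**Conclusion.** The point holds in this form: section 9.2.4 contains two unreconciled definitions. If the trial-specific one is followed, recording depends on a prior causality judgment by blinded staff, and neither the schedule nor the analysis plan secures an all-cause comparison by arm. A reader might also infer that mood changes or nightmare-related awakenings go unrecorded. They do not, because scheduled instruments measure them in both arms.

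No numerical size can be given, since the number of events lost depends on event rates and attribution habits that the documents do not state. The scope is the randomised safety comparison of up to 120 participants per arm until the crossover at Day 30. The conclusion assumes that the forms not shown contain no open adverse event question. If they do, the gap narrows to the conflicting definitions and the missing table. The efficacy analysis is unaffected. The change is worth making because the trial is meant to establish safety and the remedy is cheap.

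**What to change.** 1. In 9.2.4, replace the trial-specific sentence with one definition: all unfavourable changes in health in either arm, whatever the suspected cause.
2. Record relatedness to the device as a separate field, completed while blinded, so that it describes an event without deciding whether it is entered.
3. Ask one open adverse event question at the existing contacts (Days 7, 14, 21, 30, 60 and 90), and add the matching row to the Schedule of Activities.
4. Add to 7.5 and the SAP a table of participants with any adverse event and any serious adverse event, by randomised arm up to Day 30, with the risk difference and its 95% CI.

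The IRB reporting rules in 9.2.3, 9.2.4 and 9.3 can stay as they are, because they govern expedited reporting and not recording. The cost is a wording amendment, one short form, a few minutes of staff time across the existing contacts, and a longer event listing. No new visits are needed.

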## **9.3. Death Reporting**

Death is reported as is stated in section 8.2.3 Serious Adverse Event (SAE) Reporting.

A death that meets all three criteria for an SAE, as above, shall be reported by Study Staff to the IRB within 5 business days of learning of the death.

A detailed narrative or death letter may be requested by the sponsor including date of death, place, circumstances, cause of death, and whether the death was witnessed or not.

## **10. Informed Consent**

Subject participation in this clinical study is voluntary. Formal Consent is required from each subject and consists of a signed IRB-Approved ICF and signed IRB-Approved HIPAA. The Investigator is

responsible for ensuring that such Formal Consent is obtained prior to the use of any investigational devices, study-required procedures and/or testing, or data collection.

The obtaining and documentation of Informed Consent must be in accordance with the principles of the Declaration of Helsinki, ISO 14155, any applicable national regulations, and local IRB. The ICF must be accepted by the sponsor and approved by the site's IRB.

The IRB will provide a template of both the ICF and HIPAA documents to investigators participating in this study. Study staff will complete the templates incorporating study-specific information.

The process of obtaining Informed Consent shall at a minimum include the following steps, as well as any other steps required by applicable laws, rules, regulations and guidelines:

- be conducted by the Principal Investigator or designee authorized,
- include a description of all aspects of the clinical study that are relevant to the subject's decision to participate throughout the clinical study,
- avoid any coercion of or undue influence of subjects to participate,
- not waive or appear to waive subject's legal rights,
- use native language that is non-technical and understandable to a subject that has the equivalent of a high-school education,
- provide ample time for the subject to consider participation and ask questions, if necessary,
- ensure important new information is provided to new and existing subjects throughout the clinical study.
- The subject will be made aware that they may be in the sham arm of the trial and not receive treatment.

## **11. Protocol Deviations/Unexpected Problems Reports**

A protocol deviation is any noncompliance with the clinical trial protocol. It is the responsibility of the site investigator to use continuous vigilance to identify and report deviations within 10 working days of identification of the protocol deviation, or within 3 working days of the scheduled protocol-required activity (if the deviation/UP is discovered immediately). All deviations must be addressed in study source documents. Protocol deviations must be sent to the reviewing Institutional Review Board (IRB) per their policies. The site investigator is responsible for knowing and adhering to the reviewing IRB requirements.

Protocol deviations must also be reported in the study data collection system.

## **12. Study Discontinuation and Closure**

This study may be temporarily suspended or prematurely terminated if there is sufficient reasonable cause. Written notification, documenting the reason for study suspension or termination, will be provided by the suspending or terminating party to the principal investigator and study sponsor (if sponsor is NOT the terminating party). If the study is prematurely terminated or suspended, the Principal Investigator (PI) will promptly inform study participants, and, as necessary, the Institutional Review Board (IRB), and/or the sponsor and will provide the reason(s) for the termination or suspension. Study participants will be contacted, as applicable, and be informed of changes to their study visit schedule.

terminate

Circumstances that may warrant termination or suspension include, but are not limited to:

- Determination of unexpected, significant, or unacceptable risk to participants
- Demonstration of efficacy that would warrant stopping
- Insufficient compliance to protocol requirements
- Data that are not sufficiently complete and/or evaluable
- Determination that the primary endpoint has been met
- Determination of futility

Study may resume once concerns about safety, protocol compliance, and data quality are addressed, and satisfy the sponsor, IRB and/or Food and Drug Administration (FDA).

## **13. Data Management**

### **13.1. Data Collection and Handling**

Subject data will be recorded on REDCap electronic case report forms. MyCAP, a companion application for REDCAP, will be installed on study device phones and used by the participants to complete questionnaires throughout this study. Data will be entered with a de-identified subject indicator, with a crosswalk file to the subject identifier to be maintained by the investigating site. The electronic files will be maintained as the original study documents. All paper forms will be maintained in a locked office before being entered in the database. Once entered, the paper files will be destroyed.

De-identified data will be entered from REDCap into an SPSS database to perform data analysis.

### **13.2. Study Records Retention**

The Office of Research Development/ Office of Research Oversight (ORD/ORO" Records Control Schedule Guideline (DAA-0015-2015-0004) states:

All Protocol Files related to the review and oversight of human subjects' research protocols submitted by principal investigators to the IRB shall have a cutoff at the end of the fiscal year after the research project has been completed or terminated. Records will be retained for 6 years after the cutoff.

Records include, but are not limited to, the application to the IRB; research protocol and amendments; case reports forms; informed consent template and HIPAA Authorization template; reports of adverse events, complaints, and deviations from IRB-approved protocol; data and safety monitoring reports; research findings to date; and all relevant documents and related correspondences between the IRB and the investigators in the review of an associated protocol.

No records will be destroyed without the written consent of the sponsor, if applicable.

## 14. Abbreviations

The list below includes abbreviations utilized in this protocol.

Abbreviation	Description
AUDIT	Alcohol Use Disorders Identification Test
BMI	Body Mass Index
C-SSRS (LT)	Columbia-Suicide Severity Rating Scale-Lifetime
C-SSRS (SLC)	Columbia-Suicide Severity Rating Scale-Since Last Contact
DAST-10	Drug Abuse Screening Test - 10
DCC	Data Coordinating Center
EEG	Electroencephalogram
EHR	Electronic Health Record
ESS	Epworth Sleepiness Scale
FOSQ-10	Functional Outcomes of Sleep Questionnaire
Ha	Alternate hypothesis
HIPAA	Health Insurance Portability and Accountability Act of 1996
Ho	Null hypothesis
ICF	Informed Consent Form
ICSD-3	International Classification of Sleep Disorders – 3 rd Edition
IRB	Institutional Review Board
IRT	Image Rehearsal Therapy
ISI	Insomnia Severity Index
NCT	National Clinical Trial
N-T-F	Note-to-file
NW	NightWare
OSA	Obstructive Sleep Apnea

PCL-5	PTSD Checklist -5
PHQ-9	Patient Health Questionnaire - 9
PI	Principal Investigator
PSQI	Pittsburgh Sleep Quality Index
PSQI-A	PSQI-Addendum for PTSD
PTSD	Post-Traumatic Stress Disorder
VR-12	Veterans Rand 12 health and quality of life survey
REM	Rapid Eye Movement
SOC	Standard of Care
SPSS	Statistical Package for the Social Sciences
TNT	Traumatic Nightmares Treated
TRNS	Trauma-Related Nightmare Survey
UP	Unanticipated Problem
UPR	Unanticipated Problem Report
$\delta$	Delta (gr) – change in measurement (i.e.: PSQI)
$\sigma$	Sigma (gr) – variability (i.e.: variance)

## 15. Statement of Compliance

The trial will be conducted in accordance with International Conference on Harmonization Good Clinical Practice (ICH GCP) and applicable United States (US) Code of Federal Regulations (CFR). The Principal Investigator will assure that no deviation from, or changes to the protocol will take place without prior agreement from the sponsor and documented approval from the Institutional Review Board (IRB), except where necessary to eliminate an immediate hazard(s) to the trial participants.

The protocol, informed consent form(s), recruitment materials, and all participant materials will be submitted to the IRB for review and approval. Approval of both the protocol and the consent form must be obtained before any participant is enrolled. Any amendment to the protocol will require review and approval by the IRB before the changes are implemented to the study. All changes to the consent form will be IRB approved; a determination will be made regarding whether a new consent needs to be obtained from participants who provided consent, using a previously approved consent form.

## 17. Appendix A

Excluded Medications	Use
Verenicline	Anti-Smoking
Non-dihydropyridines	
verapamil	Calcium channel blockers --affect the heart. Reduce Heart Rate.
Diltiazem	Calcium channel blockers --affect the heart. Reduce Heart Rate.
Beta-Blockers (not ophthalmic)	Reduce blood pressure, slows heart rate.
	Treats: Heart Failure, anxiety, migraines
	May cause: Headache, depression, confusion, dizziness, NIGHTMARES, Hallucinations.
acebutolol (Sectral)	
atenolol (Tenormin)	
betaxolol (Kerlone)	
betaxolol (Betoptic S)	
bisoprolol fumarate (Zebeta)	
carteolol (Cartrol, discontinued)	
carvedilol (Coreg)	
esmolol (Brevibloc)	
labetalol (Trandate [Normodyne - discontinued])	
metoprolol (Lopressor, Toprol XL)	
nadolol (Corgard)	

nebivolol (Bystolic)	
penbutolol (Levitol)	
pindolol (Visken, discontinued)	
propranolol (Hemangeol, Inderal LA, Inderal XL, InnoPran XL)	
sotalol (Betapace, Sorine)	
Timolol (Blocadren, discontinued)	
Alpha Blockers	MUST Taper then be off med for at least 2 weeks before enrolling.

NightWare Digital Therapeutic

NightWare INC. Protocol: NW101002 Version 1.1

CLINICAL STUDY PROTOCOL TITLE: Traumatic Nightmares Treated by NightWare (To Arouse Not Awaken): A Randomized Controlled Trial

NCT NUMBER: NCT04040387

PRODUCT: NightWare Digital Therapeutic

PROTOCOL NUMBER: NW101002

STUDY SPONSOR: NightWare, INC. [name]

ORIGINAL PROTOCOL: 06 April 2023

AMENDMENT DATE: Amendment 1: 27 Jun 2023

VERSION: 1.1

CONFIDENTIALITY STATEMENT: This document is confidential. It contains proprietary information of NightWare INC. Any viewing or disclosure of such information that is not authorized in writing by NightWare INC. is strictly prohibited. Such information may be used solely for the purpose of reviewing or conducting this protocol.

Data Analysis Plan NW101002 Trial

Primary Safety Analyses The hypothesis for the primary safety endpoint is that the Active NW System will not lead to worsening of daytime sleepiness as measured by the Epworth Sleepiness Scale, which provides a score between 0 and 24 with higher values indicating a higher degree of sleepiness. Specifically, the hypothesis is that on average a user of NW will have a mean ESS score measured at 30 days following the start of NW digital therapeutic system use that is not higher than their ESS score measured at baseline. This hypothesis will be tested similarly to the primary efficacy hypothesis using a one sample t-test.

The hypothesis for the secondary safety endpoint is that the Active NW System will not lead to an increase in suicide risk as assessed by Columbia-Suicide Severity Rating Scale (C-SSRS) from baseline (Day 0) to Day 30. C-SSRS has ratings of “none”, “low”, “moderate”, and “high”. Those possible participants rated as “high” on the C-SSRS at Visit 1 will NOT qualify for the study and, if deemed necessary by the PI, will be given immediate assessment by a licensed Mental Health Provider, who will determine the next therapeutic steps. This hypothesis will be tested similarly to the primary efficacy hypothesis using a one sample t-test.

All measures used in this study will be evaluated using an intention-to-treat analysis; that is, all study participants completing the study will be included in the data analysis in the group to which they were assigned at enrollment. Additionally, a per-protocol analysis will be completed for all measures used in the study. For this analysis, use of the study device at least 50% of the study nights during the first 30 nights of the study will constitute adequate adherence to the study treatment.

The Trauma-Related Nightmare Scale questionnaire is not designed to produce a score when it is administered. The individual questions on this scale will be evaluated separately from one another.

Missing data is inevitable and can be handled in multiple ways. The data will need to be evaluated to determine the randomness of the missing data. First we will identify the distribution of the missing values and their impact then we will determine a path to deal with missing data. Depending on the impact of the missing values, we will omit participants without full data, omit missing values, impute missing values with the mean, or use multiple imputation.

Secondary and Exploratory analyses will be carried out with appropriate regression modeling techniques and hypothesis tests. In particular, we will use longitudinal data analysis methods, such as generalized estimating equations and generalized linear mixed models, to assess temporal variation in the longitudinal outcome measures, and we will carry out two sample t-tests of the secondary hypotheses. At the conclusion of the trial, the data will be assessed as both intention to treat (ITT) and per protocol. The effect sizes at the conclusion of the analyses will be compared using standard techniques. If the effect size of the per protocol analysis is greater than 10%, data will be reported as intention to treat to decrease probability of type I errors. Both analyses will follow the outline below:

Secondary outcomes, data will be presented as mean(standard deviation) or median (interquartile range), as appropriate for continuous variables. Categorical variables will be presented as frequency (percentage). Continuous data will be assessed for normality, and transformed as appropriate (e.g. log transformation, square root transformation, etc.). Patient demographics and characteristics will be listed and compared. Continuous variables will be analyzed by category, intervention vs control, by two-sided t-test or Mann-U Whitney, as appropriate. Categorical variables will be compared by Chi-Square test or Fisher's Exact test as appropriate. Longitudinal data will be analyzed by repeated measures tests as appropriate for the variables.

Repeated measure ANOVA will be used to determine the difference in responses at the time points between groups for all survey types and questions, as appropriate. If determined inappropriate Poisson regression models will be used to determine the univariate, univariable, effect size.

Upon secondary outcomes analysis, multivariable, adjusted, models will be used to determine controlled effect sizes. Each variable with a p-value of 0.25 or less in standard distribution test will be included in the model. Backward stepwise regression modeling may be used to best fit the model.

Time-to-event analyses will be conducted to determine time to survey effects over the longevity of the study (baseline, visit 2, day 30, day 60, day 90) for all survey results within the secondary outcomes. Univariate Cox regression models may be used to determine hazard ratios for the survey scores if appropriate.

Correlation coefficients (i.e. Spearman, Pearson) may be used to determine the inter-survey reliability. If determined to be reliable, multivariate analyses may be conducted for surveys.

All statistical analyses will be carried out by the Principal Investigator and/or a PhD Biostatistician.
